1.4 Overall Risk/Benefit Assessment

Ipilimumab has been the first drug to demonstrate prolonged survival in subjects with pre-treated advanced melanoma, based on a large, multinational, double-blind, pivotal, Phase 3 study⁶⁷ supported by a comprehensive Phase 2 program.

The unique immune-based mechanism of action is reflected in the clinical patterns of anti-cancer activity in some patients. Ipilimumab impacts tumor cells indirectly, and measurable clinical effects emerge after the immunological effects. Tumor infiltration with lymphocytes and the associated inflammation (documented by biopsy in some subjects) is likely the cornerstone of the effect of ipilimumab and can manifest in various patterns of clinical activity leading to tumor control. In some cases, inflammation may not be noted by radiological examination and objective response is observed with the first tumor assessment in a manner seen in patients receiving other types of anti-cancer treatments. In other cases, response may be preceded by an apparent increase in initial tumor volume and/or the appearance of new lesions, which may be mistaken for tumor progression on radiological evaluations. Therefore, in subjects who are not experiencing rapid clinical deterioration, confirmation of progression is recommended, at the

⁶⁷ Robert C, Thomas L, Bondarenko I, et al. Ipilimumab plus dacarbazine for previously untreated metastatic melanoma. N Engl J Med. 2011 Jun 30;364(26):2517-26.

investigator's discretion, to better understand the prognosis as well as to avoid unnecessarily initiating potentially toxic alternative therapies in subjects who might be benefitting from treatment. Immune-related (ir) response criteria were developed based on these observations to systematically categorize novel patterns of clinical activity and are currently being prospectively evaluated in clinical studies.

In metastatic diseases, stabilization is more common than response, and in some instances is associated with slow, steady decline in tumor burden over many months, sometimes improving to partial and/or complete responses. Thus, the immune-based mechanism of action of ipilimumab results in durable disease control, sometimes with novel patterns of response, which contribute to its improvement in OS.

The immune-based mechanism of action is also reflected in the safety profile. The most common drug-related AEs are immune-mediated, consistent with the mechanism of action of the drug and generally medically manageable with topical and/or systemic immunosuppressants. As previously discussed, the immune-mediated adverse reactions primarily involve the GI tract, skin, liver, endocrine glands, and nervous system.

The early diagnosis of immune-mediated adverse reactions is important to initiate therapy and minimize complications. Immune-mediated adverse reactions are generally manageable using symptomatic or immunosuppressive therapy as recommended through detailed diagnosis and management guidelines, as described fully in the current IB. The management guidelines for general immune-mediated adverse reactions and ipilimumab-related GI toxicities, hepatotoxicity, endocrinopathy, and neuropathy are provided in the appendices of the current IB.

In summary, ipilimumab offers clinically meaningful and statistically significant survival benefit to patients with pre-treated advanced melanoma and evidence of clinical activity in randomized studies in other tumor types. These findings, together with evidence of a safety profile that is manageable with careful monitoring and appropriate intervention for treatment of immune-mediated toxicities, suggest an acceptable benefit to risk ratio.

This clinical study will focus on patients with melanoma and brain metastases of intermediate prognosis (RPA class 2). As described earlier, the estimated prognosis of these patients is dismal. All patients are to receive the standard therapy for this condition, that is, WBRT. Ipilimumab as a single agent has shown to be active in these patients. There are biological grounds for potential synergistic efficacy. The safety of the proposed dose of Ipilimumab is well known, and there is no major concern on its use in this patient population. The safety of the combination of ipilimumab and WBRT has not been described. Given the fact that a safety data monitoring group will be defined for this study, and that the patients have a condition which clearly represents an unmet medical need, the overall risk-benefit ratio for patients entering this protocol is therefore at least comparable to and potentially better than alternative options.

1.5 **Study Rationale**

- Melanoma is the third most common cancer causing brain metastases, after cancers of the lung and breast, which appears to reflect the relative propensity of melanoma to metastasize to the central nervous system (CNS). Brain metastases are responsible for 20 to 54 percent of deaths in patients with melanoma, and among those with documented brain metastases, these lesions contribute to death in up to 95 percent of cases, with an estimated median overall survival ranging between 1.8 and 10.5 months, depending upon other prognostic factors.^{2,3,5,6,7,8,9,11}

- Ipilimumab is an anti-CTLA4 monoclonal antibody that has demonstrated a clinically relevant and statistically significant improvement in overall survival, either alone (second line)⁶⁷ or in combination with DTIC (1st line).⁶⁸
- Ipilimumab has shown activity against brain metastases.^{1,16,17}
- According to the EMA-approved label for Yervoy[®], the use of glucocorticoids at baseline (commonly prescribed when brain metastases are diagnosed) should be avoided before the administration of ipilimumab. Data show that the use of even high doses of glucocorticoids for the management of immune-related adverse events do not decrease the efficacy of Yervoy[®]. There is no documented experience on the efficacy of Yervoy[®] when given concomitantly with radiation therapy and glucocorticoids.⁶⁹
- In experimental models, radiation therapy is synergistic to anti-CTLA-4 strategies (abscopal effect).^{41,42,43}
- There are no published results from clinical trials on the interaction between radiation therapy and ipilimumab.

2 STUDY OBJECTIVES

2.1 Primary Objective.

- Efficacy - Primary endpoint: 1-year survival rate

2.2 Secondary Objectives

- Efficacy – Endpoints:
 - Progression-Free survival-PFS (median, 6-month PFS rate)
 - Intracranial PFS (median, 6-month PFS rate)
 - Extracranial PFS (median, 6-month PFS rate)
 - Overall survival (median)
 - Response rate: (global, intracranial, extracranial) (“Immune-related response criteria”)
- Safety: Adverse Event rates
- Feasibility: dose delays/reductions, treatment exposure

2.3. Exploratory Objectives.

- Potential baseline predictors of efficacy (in tumour tissue and peripheral blood – see 6.4.3.)
- Potential early surrogates for response: inpatient variation of quantitative apparent diffusion coefficients of serial diffusion-weighted magnetic resonance imaging

⁶⁸ Hodi FS, O'Day SJ, McDermott DF, et al. Improved survival with ipilimumab in patients with metastatic melanoma. *N Engl J Med.* 2010 Aug 19;363(8):711-23.

⁶⁹ http://www.ema.europa.eu/docs/en_GB/document_library/EPAR_-_Product_Information/human/002213/WC500109299.pdf

3 **STUDY DESIGN**

This is a non-controlled, single stage, multicenter phase 2 clinical study. A total of 56 evaluable patients will be treated in this study.

- Main eligibility criteria are: patients with melanoma and brain metastases, adequately fit (ECOG PS 0 to 1; Barthel Index > 10/20) and of intermediate prognosis according to the RPA classification (Table 1). These patients must not have cerebral metastases for which local therapy (neurosurgery, radiosurgery) might achieve a disease-free status; they must not be experiencing a rapid clinical deterioration, risk of herniation; patients must not require unstable ascending dosing of supportive medication in the last week -including anti-convulsivants, steroids and analgesics-, or dexamethasone > 16 mg/day (or other glucocorticoid at an equivalent dose); patients must not have a high LDH (> 2 x ULN), they must not have an uncontrolled diabetes mellitus (HbA1c > 9%) and must be suitable for receiving an anti CTLA4 (i.e. not having any autoimmune-mediated co-morbidities). Patients must have not received prior therapy for brain metastases. Screening stage: Once the ICF is signed by the patient and investigator, patients will be sequentially registered at the Spanish Melanoma Group Datacenter or delegated CRO, by submitting a “registration form”. A Patient Identification Number will be provided by the Sponsor. A second form, the “eligibility checklist”, will be sent by the investigational site once the screening phase has been completed, either if the patient becomes eligible or if he/she results in a screening failure. No protocol exceptions will be permitted by the sponsor.

Patient inclusion:

[figure not shown]
After confirming that a patient is a candidate for inclusion in this study (inclusion / exclusion), the subject will be assigned a code of patient centralized (registration or inclusion of patients).

The process of enrolling patients described below:

1. Complete and sign the inclusion of the patient (the registration form must be signed by a clinical Principal Investigator or designated appropriately identified in the list of signatures and recording studio delegation of responsibilities).
2. Send the completed and signed form to:

██
██

3. ██████████ will register the patient and
 4. will send the inclusion confirmation form to the site, both by fax and email. Confirmation of patient inclusion will contain the patient number, which identifies subjects in the trial.
 5. Once the site has received the confirmation of inclusion for the patient, the patient can begin receiving protocol treatment.
- The trial schema is represented in the following figure:

All individual patient registered into the trial should undergo the screening phase of the study. Patients consenting, registered and eligible will subsequently proceed through the treatment and follow up phases of the trial.

- **Screening Phase**

- It initiates after the written informed consent is obtained and the patients is registered. In this phase the assessment of the subject's eligibility to participate will be done, as determined by the inclusion/exclusion criteria.

- **Treatment Phase**

- Treatment will consist in the administration of ipilimumab and WBRT. The dose of ipilimumab will be 3 mg/kg, administered intravenously over a 90-minute period every 3 weeks, for a total of four doses. Standard WBRT should be initiated between the first and second dose of ipilimumab. The dose of radiation therapy will be 30 Gy over 10 fractions. Radiobiologically equivalent doses might be acceptable, but require discussion and approval of the Sponsor.
- Laboratory evaluations should be performed and the results examined before administration of each ipilimumab dose, with the exception of hormone results. For these latter parameters it is required that at least the results of the tests performed within the last 3 weeks are available and normal.
- As durable disease stabilization and/or objective tumor response can be seen after early progression before Week 12, it is recommended that, in the absence of dose-limiting toxicities

(eg, serious immune-mediated adverse reactions), all four doses of ipilimumab be administered over the initial 12 weeks even in the setting of apparent clinical progression, providing the subject's performance status remains stable.

- All subjects who enter the treatment period, including those who may have discontinued treatment for drug-related AEs and/or who have evidence of clinical progression during the induction period, should obtain a 12-week tumor assessment.
- Based on clinical experience in the ongoing and completed melanoma studies, the following recommendations apply for subject management in light of the Week 12 or later tumor assessments:
 - The appearance of new lesions in subjects with other stable or shrinking baseline tumor burden may be experiencing clinical benefit and should continue in follow-up and/or maintenance therapy before alternative anti-cancer agents are considered. These subjects can be seen to have continued tumor shrinkage in follow-up scans.
 - As long as overall tumor burden is stable or decreasing, subjects should remain in follow-up, even in the presence of new lesions.
 - Clinical progression warranting alternative anti-cancer treatment should be considered only in subjects whose overall tumor burden appears to be substantially increased and/or in subjects whose performance status is decreased.
- **Follow-up** (duration of study).
 - Subjects who are no longer receiving ipilimumab because of unacceptable toxicity (refractory Grade > 3 immune-mediated adverse reactions) or due to investigator judgment are managed in follow-up. Efficacy assessments for these subjects during follow-up are as per the standard of care. Date of death is recorded.
 - Subjects who discontinue ipilimumab treatments should be followed until death or the closure of the study (whichever is first).
 - Subjects who are no longer receiving ipilimumab because of clinical progression and who have switched to alternative treatment are not followed formally except to record the date of death.

Study duration:

- For each individual patient, the maximal duration of the treatment period is 4 cycles of ipilimumab. Patients will be followed up until death or trial termination (whatever comes first), for a maximum of 36 months. The study will be terminated 18 months after the last patient received the first dose of ipilimumab.

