Hepatic immune-related AEs were mostly clinically silent and manifested as transaminase or bilirubin laboratory abnormalities. Fatal hepatic failure has been reported in clinical trials of ipilimumab. Serum transaminase and bilirubin levels must be evaluated before each dose of ipilimumab as early laboratory changes may be indicative of emerging immune-related hepatitis. Elevations in liver function tests (LFTs) may develop in the absence of clinical symptoms. Increase in LFT or total bilirubin should be evaluated to exclude other causes of hepatic injury, including infections, disease progression, or medications, and monitored until resolution. Liver biopsies from patients who had immune-related hepatotoxicity showed evidence of acute inflammation (neutrophils, lymphocytes, and macrophages).

Immune-related Skin Toxicity

Skin immune-related AEs presented mostly as a rash and/or pruritus. Some subjects reported vitiligo associated with ipilimumab administration. Fatal toxic epidermal necrolysis has been reported in clinical trials of ipilimumab.

Immune-related Endocrinopathy

Ipilimumab can cause inflammation of the endocrine system organs, specifically hypophysitis, hypopituitarism, and adrenal insufficiency and patients may present with nonspecific symptoms, which may resemble other causes such as brain metastasis or underlying disease. The most common clinical presentation includes headache and fatigue. Symptoms may also include visual field defects, behavioral changes, electrolyte disturbances, and hypotension. Adrenal crisis as a cause of the patient's symptoms should be excluded. Based on the available data with known outcome, most of the subjects symptomatically improved with hormone replacement therapy. It is possible that long-term hormone replacement therapy will be required for subjects developing hypophysitis/hypopituitarism after treatment with ipilimumab.

Immune-related Neurological Events

Neurological manifestations included muscle weakness and sensory neuropathy. Fatal Guillain-Barré syndrome has been reported in clinical trials of ipilimumab. Patients may present with muscle weakness. Sensory neuropathy may also occur. Unexplained motor neuropathy, muscle weakness, or sensory neuropathy lasting more than 4 days should be evaluated and non-inflammatory causes such as disease progression, infections, metabolic syndromes, and medications should be excluded.

Other Immune-related AEs

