6. STUDY PROCEDURES AND OBSERVATIONS

6.1. Time and Events Schedule (Table 12)

Visit	Visit 1 Registration (Day -28 to day -1)	Visit 2 Eligibility (Day -7 to day -1)	Visit 3. C1D 1	Visits R.1 to R.x Starting Between C1D2 and C2D1	Visit 4 C2D 1	Visit 5 C3D 1	Visit 6 C4D 1	End of treatment C4D30(±2)	Follow-up Tumor Assesment (every 9 weeks +/- 1)	Follow up visits Months 6, 9, 12, 15, 18, 21, 24, 27, 30 (+/- 1 week)
Informed Consent Form	X									
Central registration	X									
Medical History		X(1)								
Concomitant diseases		X(1)	X	X	X	X	X	X		X
Symptoms		X	X	X	X	X	X	X		X
Karnofsky PS,Barthel Index, Physical exam, vital constants, body weight		X	X	X	X	X	X	X		X
Neurological exam		X	X	X	X	X	X	X		X
Concomitant medications		X	X	X	X	X	X	X		X
RPA class		X								
Inclusion/Exclusion checklist		X								
Eligibility communication		X								
Blood Workup										
Hematology		X		X	X	X	X	X		X
Biochemistry		X		X	X	X	X	X		X
Pregnancy test		X(2)			X	X	X	X		
Auto-immunity panel		X(1)								
Hormones (morning cortisol and ACTH, free T4, T3, TSH, prolactin)		X(1)			X	X	X	X		X
Efficacy evaluation										

GRAY-B Study (GEM 1202). V1.0 (28 Nov 2013)

Chest-Abdomen-pelvis CT scan		X(1)						X(5)	X	X
Craneal CT scan/MRI		X(1)						X(5)	X	X
Safety evaluation										
Adverse events /SAEs	Throughout the study									
Dose reductions					Throughout the study, when applicable					
Dose delays					Throughout the study, when applicable					
Biomarker evaluation (optional)										
Archived tumour tissue		X(1)								
Peripheral blood (serum + whole blood)			X		X	X	X	X		
DW-MRI (optional)		X(3)				X(4)		X		
Intervention										
Ipilimumab infusion			C1		C2	C3	C4			
Initiation of radiation therapy				X						

(1) Can be performed between d-28 and d-1.

(2) All WOCBP MUST have a negative pregnancy test within 72 hours before receiving ipilimumab. The minimum sensitivity of the pregnancy test must be 25 IU/L or equivalent units of HCG. If the pregnancy test is positive, the subject must not receive ipilimumab and must not be enrolled in the study.

(3) If done, it should be performed up to 2 weeks prior to C1D1

(4) If applicable, 4 weeks (± 1) after the end of WBRT

(5) Should be done on week 12+1

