End of treatment visit (EOT) will take place 30 + 2 days after the last dose of ipilimumab. This visit will require a complete evaluation of patient's symptoms, Karnofsky/Barthel scores, physical exam (including weight, vital constants and neurological exam), lab tests, collection of AEs and of concomitant medication. If the disease was not evaluated before, EOT visit should include a body and cranial CTscan/MRI.

6.2.1.e Follow-up visits.

Per protocol, the disease should be evaluated until death or confirmed progression (mWHO/immune response criteria). Tumor assessment will be performed with CT/MRI of brain, chest, abdomen and pelvis at baseline, at weeks 12 and 17 \pm 1 and then, every 9 \pm 1 weeks. The same method of assessment (CT or MRI) should be used throughout the patient's time on study for consistent evaluation of response.

After EOT visit, the occurrence of new SAEs and irAEs will be reported up to 90 days after last ipilimumab administration. Ongoing SAEs/irAEs will be followed up until recovery.

Survival status will be checked at week 12, 16-18 and then, every 8-10 weeks.

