Laboratory tests are obtained as part of screening and to determine eligibility. Results of safety laboratory collections (ie, Chemistry and Hematology) must be obtained and reviewed in advance of study drug dosing.

- The following lab parameters must be collected within a window of up to 1 day prior to dosing: CBC/diff (includes ANC and ALC), AST, ALT, total bilirubin, CRP, sodium, chloride, bicarbonate, BUN

or urea, creatinine, and glucose. Baseline values up to 7 days before the first dose are acceptable prior to C1. These lab tests will also be performed at week 12, EOT, and 90 days after last dose administration of ipilimumab (+/-1 week).

- CBC/diff, AST, ALT, total bilirubin, sodium, chloride, BUN or urea, creatinine, and glucose will also be collected weekly during WBRT

All protocol-specified laboratory tests will be analyzed and reported by a local lab.

Importantly, **LFT results (AST, ALT, and total bilirubin) must be reviewed within 24 h prior to dosing**. If abnormal LFTs are detected, the subject must be managed using the hepatotoxicity algorithm in the SMPC. (Additional draws must be incorporated when monitoring recovery from any non-hematologic AE (eg, elevations in ALT, AST).

6.4.1.f Endocrine Tests

The following endocrine tests should be performed at Screening and prior to each dosing visit: TSH, free T4 and T3, morning ACTH and cortisol, and prolactin.

Other hormones might be tested as well as clinically indicated.

During treatment, if patient is asymptomatic, it will be adequate to confirm at least the normality of the results of the tests performed within the last 3 weeks. If the patient is symptomatic (e.g. asthenia, cephalgia) it will be mandatory to check the results of the pre-dose testing (at least 72 h prior to dose administration)

6.4.1.g HIV and Hepatitis Panel

At screening, testing for HIV, hepatitis C antibody, and hepatitis B surface antigen (HBsAg) should be performed for clinically suspected HIV, HBV, and HCV. If positive results at Screening are not indicative of true active or chronic infection, the subject may enter the study after discussion and agreement between the Investigator and the Medical Monitor. These tests will be repeated during the course of the study if clinically indicated.

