8.3.1. Serious Adverse Events

The following information is provided to investigators for either inclusion in protocol documents or other related study documents. It will also be contained in the Study Agreement:

Following the subject’s written consent to participate in the study, all SAEs must be collected, including those thought to be associated with protocol-specified procedures. All SAEs must be collected that occur

within 90 days of discontinuation of dosing of the investigational product. If applicable, SAEs must be collected that relate to any later protocol-specified procedure (eg, a follow-up skin biopsy). The investigator should notify the Sponsor of any SAE occurring after this time period that is believed to be related to the investigational product or protocol-specified procedure.

All SAEs whether related or unrelated to the ipilimumab, must be immediately reported to the Sponsor or delegated CRO (by the investigator or designee) within 24 hours of becoming aware of the event. If only limited information is initially available, follow-up reports are required. The original SAE form must be kept on file at the study site.

All SAEs should be immediately reported to CRO:

[REDACTED]

Suspected Unexpected Serious Adverse Reactions (SUSAR) will be reported by the study Sponsor to the relevant Authorities and into the Eudravigilance database. The Sponsor will be provided with a simultaneous copy of all adverse events filed with the Authorities.

Serious adverse events, whether related or unrelated to investigational product, must be recorded on the SAE page and reported expeditiously to the Sponsor (or designee) to comply with regulatory requirements. An SAE report should be completed for any event where doubt exists regarding its status of seriousness.

All SAEs must be immediately reported by confirmed facsimile transmission (fax) and mailing of the completed SAE page. In some instances where a facsimile machine is not available, overnight express mail may be used. If only limited information is initially available, follow-up reports are required. (Note: Follow-up SAE reports should include the same investigator term(s) initially reported.) In selected circumstances, the protocol may specify conditions that require additional telephone reporting.

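### The protocol contradicts itself on safety collection in the 90 days after the last ipilimumab dose: Section 3 limits follow-up after progression and a switch to date of death, and Table 12 has no visit for the 90-day laboratory tests

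*Protocol*

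**What the plan says.** **Follow-up after a switch.** The Follow-up part of protocol Section 3 ends with a bullet on patients who are off ipilimumab for clinical progression and have moved to another treatment. They "are not followed formally except to record the date of death". The bullet just before it has everyone who discontinues ipilimumab followed to death or study closure, without saying what that follow-up contains.

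**The 90-day safety period.** Section 6.2.1.e says that, after the end-of-treatment (EOT) visit, "the occurrence of new SAEs and irAEs will be reported up to 90 days after last ipilimumab administration". Section 8.3.1 requires all SAEs "within 90 days of discontinuation of dosing of the investigational product". Section 8.3.3 extends the collection of nonserious immune-related events to the same limit. Section 9.4.3 sets the safety reporting period for all treated subjects from first dose to 90 days after the last. None of these makes an exception for patients who switch.

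**The 90-day laboratory tests.** Section 6.4.1.e asks for the safety panel at week 12, at EOT and 90 days (±1 week) after the last dose. Table 12 has no 90-day column. After EOT it has a tumour-assessment column, in which only the two imaging rows are marked, and then follow-up visits with examination and blood tests starting at month 6. Its AE/SAE row is marked as running throughout the study.

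**The concern.** Sites have to act on one of two instructions. A site that applies the Section 3 bullet as written stops collecting events once a patient has progressed and switched. A site that works from Table 12 has no prompt for the 90-day blood tests.

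Adverse event rates are a secondary objective, and Section 1.4 says that the safety of ipilimumab with whole-brain radiotherapy has not been described. Protocol Section 9.4.3 and SAP Sections 1.6 and 1.7 report safety on treated patients, and the SAP table shells give crude percentages. A patient whose collection stopped early therefore counts as fully observed, and a missed event can only lower the rate.

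The laboratory gap matters separately. The protocol's own safety summary says: "Hepatic immune-related AEs were mostly clinically silent and manifested as transaminase or bilirubin laboratory abnormalities". Events of that kind are not reliably picked up by open-ended AE reporting.

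**Working it through.** **The plan's own figure.** Section 9.4.3 describes 90 days as more than 5 half-lives. With the terminal half-life of 14.7 days in Section 1.3.3.b, 5 × 14.7 = 73.5 days and 90 / 14.7 = 6.1 half-lives. The statement reproduces, so the 90-day period is deliberate and consistent with the pharmacokinetics.

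**Calendar inputs.** First dose = day 1. Dosing is every 3 weeks for four doses (Section 3). EOT is C4D30 in Table 12, and 30 days after the last dose in Section 6.2.1.d. Laboratory tests are due at 90 days ±7 (Section 6.4.1.e). The first follow-up visit is month 6 ±1 week (Table 12), taken here as 26 weeks.

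**On-schedule patient.**
- Fourth dose: 1 + 3 × 21 = day 64.
- EOT: day 93 (C4D30) or day 94 (30 days after the dose).
- 90-day point: 64 + 90 = day 154. Laboratory window: days 147 to 161.
- Month 6: 1 + 182 = day 183. Visit window: days 176 to 190.
- Shortfall: 176 − 161 = 15 days. The earliest month-6 visit comes 15 days after the laboratory window closes.
- Part of the 90 days after EOT with no scheduled examination or laboratory visit: 154 − 94 = 60 days.

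**Other last doses.**

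| Last dose | Day | 90-day point | Laboratory window |
|---|---|---|---|
| C1 | 1 | 91 | 84–98 |
| C2 | 22 | 112 | 105–119 |
| C3 | 43 | 133 | 126–140 |
| C4 | 64 | 154 | 147–161 |

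All four windows close before day 176. For a patient given one dose only, the week-12 tests in Section 6.4.1.e (1 + 84 = day 85) happen to fall in the window. A delayed last dose reaches the month-6 visit only if given on about day 79 or later (176 − 97) for the laboratory window, or day 86 or later (176 − 90) for the 90-day limit itself. Section 5.1.5.a allows the course to run to 18 weeks (1 + 126 = day 127), so such patients can exist, but they are not the planned case.

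**Effect of a switch after four on-schedule doses.** Two illustrative dates are day 91, shortly after the week-12 scan, and day 119, four weeks later, which allows for confirmation of progression.
- Day 91: 154 − 91 = 63 of 90 days uncollected (70%).
- Day 119: 154 − 119 = 35 of 90 days uncollected (39%).

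**The case against.** The strongest reply is that the safety sections are specific and mandatory. Section 8.3.1 says that all SAEs in the period must be collected, and Section 6.3.2 has AEs and SAEs reported up to and including follow-up visits. The Section 3 bullet does not mention adverse events, and a neighbouring bullet deals with efficacy assessments, so it can be read as ending tumour follow-up only. That reading is reasonable, and it may be what was meant. It is not what the sentence says, because date of death is given as the sole exception.

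A reader might infer from Table 12 that there is no safety contact at all between EOT and month 6. The documents do not support that. The AE/SAE row runs throughout the study, and Section 6.2.1.e places a survival check at weeks 16 to 18 and imaging at week 17 ±1 in that interval. What is missing is a scheduled laboratory or examination visit. The whole interval should not be counted either: of the 89 days from day 94 to day 183, only 60 lie inside the 90-day period.

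A reader might also try to size the affected group from the 44.4% best response of progressive disease in CA184024 (Table 9). That is a best response over the whole study, not a week-12 result. It comes from 10 mg/kg with dacarbazine in previously untreated disease. The bullet also needs both progression and a switch, and Section 3 reserves alternative treatment for substantially increased tumour burden or reduced performance status.

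One further point limits the size of the bias. Section 1.3.4 says that immune-related events commonly start 3 to 10 weeks after the first dose. Ten weeks is day 71, before EOT, so most first onsets would already be captured.

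**Conclusion.** Both contradictions stand. The Section 3 bullet cannot be applied literally together with Sections 6.2.1.e, 8.3.1, 8.3.3 and 9.4.3, and an on-schedule patient has no Table 12 visit that can hold the tests required by Section 6.4.1.e.

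For one patient given all four doses on schedule, the loss under Section 3 is 63 of 90 days with a switch on day 91 and 35 of 90 with a switch on day 119. The first is close to the worst case, because it allows no time for a confirmatory scan. Any resulting bias in the reported SAE and immune-related event rates is downwards. Its size cannot be computed: the documents give no switching rate and no rate of events starting after EOT. The primary endpoint is unaffected, since date of death is still recorded.

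These results assume 21-day cycles without delay, month 6 taken as 26 weeks, and sites that follow Section 3 or Table 12 to the letter. This should be corrected, but it does not threaten the trial's main conclusion.

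**What to change.** The sponsor should reconcile the passages.

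- **Section 3:** state that the limit on formal follow-up after a switch does not override the 90-day SAE and immune-related event collection already required elsewhere. Record the start date of the new therapy.
- **Table 12:** align it with the 90-day (±1 week) laboratory tests already required by Section 6.4.1.e, counted from the patient's actual last dose.

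The cost is protocol wording and one schedule column, plus one date on the case report form. No new test is introduced. The small downside is that some events after a switch will be due to the new therapy. With the start date recorded, the safety tables can show events before and after the switch separately.
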